## Synopsis

Study Number:	ER 18/282
Protocol Title:	Comparative Study of Antimicrobial Effectiveness Evaluation of 26 ml Project X, 5.1ml Project X and Prevantics® Maxi Swabstick following ASTM E1173
Planned Sample Size:	This evaluation will be performed with an estimated of a minimum of 75 evaluable subjects corresponding to 50 evaluable sites per product with qualifying treatment day microbial baseline counts per body area (abdomen and groin).
Study Design:	This is a randomized, single-center, single blind study in healthy subjects. The staff member(s) performing bacterial enumeration will be blinded from the identification of treatment assignment.
Study Methodology:	ASTM Standard Test Method E1173-15
Study Population:	Healthy subjects at least 18 years of age and of any race. Screening Day Baseline microbial count requirements are at least $3.11 \log_{10}$ CFU/cm  bilaterally on the abdomen, and at least $5.00 \log_{10}$ CFU/cm  bilaterally on the groin except for subjects enrolled for Neutralization study. Treatment Day Baseline microbial count requirements are in the range of $3.11$ to $5.50 \log_{10}$ CFU/cm  , inclusive, on the abdomen, and $5.00$ to $7.50 \log_{10}$ CFU/cm  , inclusive, on the groin except for subjects enrolled for Neutralization study.
Objectives:	
Efficacy objectives
 
The objective of this study is to demonstrate immediate (30 seconds and 10 minutes) and persistent (6 hours) antimicrobial efficacy for patient preoperative skin preparation of product A and product B compared with product C. To demonstrate the immediate antimicrobial efficacy at 10 minutes post-application the following criteria should be met on both body area (abdomen and groin):
 
 
- non-inferiority of the ATE of the product A and product B compared to product C (the upper two-sided 95% confidence bound of the post-application microbial counts corrected for Baseline of the A-C or B-C should be less than <math>0.5 \log_{10}</math>).
 
 
To demonstrate the persistent efficacy for patient preoperative skin preparation, the microbial counts (<math>\log_{10}</math> CFU/cm^2) at 6 hours post-application should be lower than or equal to the baseline for 100 percent of the subjects in each body area.
 
Safety objectives
 
Safety will also be evaluated based on the incidence of adverse events reported during the study and assessment of skin irritation ratings.

Study Endpoints:	
 
- <math>\log_{10}</math> CFU/cm^2 of skin flora at the abdominal and groin sites before and after each treatment at 30 seconds, 10 minutes and 6 hours.
 
- Skin irritation scores (Erythema, Edema, Rash, and Dryness) at each time interval and the incidence of AEs reported during the study.
 

Study Products:	
  
 Treatment	Description	Body Site	Application Time	Drying Time	Treatment Area	
   
 A – 26 ml Project X	3.15 % w/v chlorhexidine gluconate / 70% v/v isopropyl alcohol, applied back and forth	Abdomen	30 seconds	min. 180 seconds	5.0" x 5.0" (12.7 cm x 12.7 cm)	
 
 		Groin	120 seconds	min. 180 seconds	1.5" x 5.0" (3.81 cm x 12.7 cm)	
 
 B – 5.1 ml Project X	3.15 % w/v chlorhexidine gluconate / 70% v/v isopropyl alcohol, applied back and forth	Abdomen	30 seconds	30 seconds	5.0" x 5.0" (12.7 cm x 12.7 cm)	
 
 		Groin	120 seconds	90 seconds	1.5" x 5.0" (3.81 cm x 12.7 cm)	
 
 C – 5.1ml Prevantics® Maxi Swabstick	3.15 % w/v chlorhexidine gluconate / 70% v/v isopropyl alcohol, applied back and forth	Abdomen	30 seconds	30 seconds	5.0" x 5.0" (12.7 cm x 12.7 cm)	
 
 		Groin	120 seconds	90 seconds	1.5" x 5.0" (3.81 cm x 12.7 cm)	
  
						Treatment	Description	Body Site	Application Time	Drying Time	Treatment Area	A – 26 ml Project X	3.15 % w/v chlorhexidine gluconate / 70% v/v isopropyl alcohol, applied back and forth	Abdomen	30 seconds	min. 180 seconds	5.0" x 5.0" (12.7 cm x 12.7 cm)			Groin	120 seconds	min. 180 seconds	1.5" x 5.0" (3.81 cm x 12.7 cm)	B – 5.1 ml Project X	3.15 % w/v chlorhexidine gluconate / 70% v/v isopropyl alcohol, applied back and forth	Abdomen	30 seconds	30 seconds	5.0" x 5.0" (12.7 cm x 12.7 cm)			Groin	120 seconds	90 seconds	1.5" x 5.0" (3.81 cm x 12.7 cm)	C – 5.1ml Prevantics® Maxi Swabstick	3.15 % w/v chlorhexidine gluconate / 70% v/v isopropyl alcohol, applied back and forth	Abdomen	30 seconds	30 seconds	5.0" x 5.0" (12.7 cm x 12.7 cm)			Groin	120 seconds	90 seconds	1.5" x 5.0" (3.81 cm x 12.7 cm)
Treatment	Description	Body Site	Application Time	Drying Time	Treatment Area																																											
A – 26 ml Project X	3.15 % w/v chlorhexidine gluconate / 70% v/v isopropyl alcohol, applied back and forth	Abdomen	30 seconds	min. 180 seconds	5.0" x 5.0" (12.7 cm x 12.7 cm)																																											
		Groin	120 seconds	min. 180 seconds	1.5" x 5.0" (3.81 cm x 12.7 cm)																																											
B – 5.1 ml Project X	3.15 % w/v chlorhexidine gluconate / 70% v/v isopropyl alcohol, applied back and forth	Abdomen	30 seconds	30 seconds	5.0" x 5.0" (12.7 cm x 12.7 cm)																																											
		Groin	120 seconds	90 seconds	1.5" x 5.0" (3.81 cm x 12.7 cm)																																											
C – 5.1ml Prevantics® Maxi Swabstick	3.15 % w/v chlorhexidine gluconate / 70% v/v isopropyl alcohol, applied back and forth	Abdomen	30 seconds	30 seconds	5.0" x 5.0" (12.7 cm x 12.7 cm)																																											
		Groin	120 seconds	90 seconds	1.5" x 5.0" (3.81 cm x 12.7 cm)																																											
Statistical Methods:	
Subjects with treatment day baseline bacterial count in the range of 3.11 to 5.50 <math>\log_{10}/\text{cm}^2</math>, inclusive, on the abdomen and 5.00 to 7.50 <math>\log_{10}/\text{cm}^2</math>, inclusive, on the groin will be included in the analysis.
 
An alpha level of 5% will be used for all analyses.
 
The following descriptive statistics for <math>\log_{10} \text{CFU}/\text{cm}^2</math> and for <math>\log_{10} \text{CFU}/\text{cm}^2</math> reductions from Baseline will be computed for each treatment, grouped by body area and each post application sampling time point (30 seconds, 10 minutes and 6 hours): mean, median, standard deviation, minimum, maximum, and count.
 
Efficacy Analysis
 
A linear regression model for each body area (abdomen and groin) and each post-treatment sampling time point of immediate efficacy (30 seconds and 10 minutes post-application) will be used. In the model, the dependent variable used will be the post-treatment bacterial count (<math>\log_{10} \text{CFU}/\text{cm}^2</math>) and predictors will be the treatment as a fixed effect and the Baseline as a covariate. The ATE corrected for Baseline will be estimated from the model and compared to non-inferiority criteria.
 
To evaluate the persistent efficacy (6 hours post-application) of the product A and B, microbial counts (<math>\log_{10} \text{CFU}/\text{cm}^2</math>) at 6 hours post-application for each product application site will be converted to a binary (success/failure), "success" defined as having microbial counts less than or equal to the baseline counts. Responder rates
																																															

	
at 6 hours post product application will be summarized descriptively for each product on each body area.
 
Safety Analysis
 
All treated subjects will be considered evaluable for safety. Skin irritation scores will be reported for any subject who is scored with a 1 or more at any observation (baseline screening day, baseline treatment day, post-application/prior to 30 seconds, 10 minutes, and 6 hours sampling procedures), in any category for any site. Adverse events (including post treatment skin irritation scores of 3), will also be summarized. Summary tables will present incidence rates of adverse events by treatment group for all subjects who enter the treatment period. Listings of adverse events will be provided.

--	--

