## 2 Study Objectives

### 2.1 Efficacy objectives

The objective of this study is to demonstrate immediate (30 seconds and 10 minutes) and persistent (6 hours) antimicrobial efficacy for patient preoperative skin preparation of product A and product B compared with product C.

To demonstrate the immediate antimicrobial efficacy at 30 seconds and 10 minutes post-application the following criteria should be met on both body area (abdomen and groin):

- non-inferiority of the ATE of the product A and product B compared to product C (the upper two-sided 95% confidence bound of the post-application microbial counts corrected for Baseline of the A-C or B-C should be less than  $0.5 \log_{10}$ ).

To demonstrate the persistent efficacy for patient preoperative skin preparation, the microbial counts ( $\log_{10}$  CFU/cm^2) at 6 hours post-application should be lower than or equal to the baseline for 100 percent of the subjects in each body area.

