## 6 Assessment of Efficacy

### 6.1 Efficacy Parameters

The measure of antimicrobial efficacy will be the  $\log_{10}$  CFU/cm^2 of skin flora at the abdominal and groin sites 30 seconds, 10 minutes and 6 hours following study products application relative to the Treatment Day baseline  $\log_{10}$  counts.

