### 9.2 Sample Size

This evaluation will be performed with an estimated of a minimum of 75 evaluable subjects corresponding to 50 evaluable sites per product with qualifying treatment day microbial baseline counts per body area (abdomen and groin). No sample size calculation was performed to provide statistically-powered evidence of efficacy as part of this study.

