#### 9.3.1 Efficacy Analysis

A linear regression model for each body area (abdomen and groin) and each post treatment sampling time point of immediate efficacy (30 seconds and 10 minutes post-application) will be used. In the model, the dependent variable used will be the post treatment bacterial count ( $\log_{10}$  CFU/cm^2) and predictors will be the treatment as a fixed effect and the Baseline as a covariate. The ATE corrected for Baseline will be estimated from the model and compared to non-inferiority criteria.

To evaluate the persistent efficacy (6 hours post-application) of the product A and B, microbial counts ( $\log_{10}$  CFU/cm^2) at 6 hours post-application for each product application site will be converted to a binary (success/failure), "success" defined as having microbial counts less than or equal to the baseline counts. Responder rates at 6 hours post product application will be summarized descriptively for each product on each body area.

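### The Synopsis sets the immediate-efficacy non-inferiority criterion at 10 minutes only; Section 2.1 sets it at 30 seconds and 10 minutes

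*Combined protocol and SAP*

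**What the plan says.** The Synopsis, under Objectives, first defines the aim: "The objective of this study is to demonstrate immediate (30 seconds and 10 minutes) and persistent (6 hours) antimicrobial efficacy". The next sentence gives the criterion: "To demonstrate the immediate antimicrobial efficacy at 10 minutes post-application the following criteria should be met on both body area". The condition is that the upper limit of the two-sided 95% interval for A minus C, or B minus C, adjusted for baseline, lies below 0.5 log10.

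Section 2.1 carries the same objective and condition but introduces the condition with "To demonstrate the immediate antimicrobial efficacy at 30 seconds and 10 minutes post-application the following criteria should be met on both body area".

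The analysis text covers both times. The Synopsis statistical methods describe a model for "each post-treatment sampling time point of immediate efficacy (30 seconds and 10 minutes post-application) will be used", and Section 9.3.1 does the same ("time point of immediate efficacy (30 seconds and 10 minutes post-application) will be used"). Section 9.3.1 then says: "The ATE corrected for Baseline will be estimated from the model and compared to non-inferiority criteria". The Synopsis has the same sentence. Neither place repeats the times at which the criteria must be met. Section 6.1 measures efficacy at "30 seconds, 10 minutes and 6 hours following study products application relative to the Treatment Day baseline" counts. On sample size, Section 9.2 states: "No sample size calculation was performed to provide statistically-powered evidence of efficacy as part of this study".

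**The concern.** The 0.5 log10 comparison is the only inferential success rule in the plan. The 6-hour result is judged by a responder rate that is summarized descriptively. A rule of that weight should have one reading, and here it has two.

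One pattern of results separates them: a product meets the bound at 10 minutes on abdomen and groin but misses it at 30 seconds on at least one. That product meets the criterion as the Synopsis writes it and fails the criterion as Section 2.1 writes it. If the conflict is still open when results are known, the rule can be chosen to suit them. Under Section 3.3 only the enumeration staff are blinded, and their raw data sheets are joined to the rest of the case report form once recording is complete. The wording should be settled before that point.

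**Working it through.** **1. The texts side by side**

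| Place | Role | Times covered |
|---|---|---|
| Synopsis, Objectives, first sentence | aim | 30 seconds, 10 minutes (and 6 hours for persistence) |
| Synopsis, Objectives, criterion | success rule | 10 minutes |
| Section 2.1, criterion | success rule | 30 seconds and 10 minutes |
| Synopsis, Statistical Methods | models, compared with the criteria | 30 seconds and 10 minutes |
| Section 9.3.1 | models, compared with the criteria | 30 seconds and 10 minutes |
| Section 6.1 | efficacy measure | 30 seconds, 10 minutes, 6 hours |

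Only the Synopsis criterion leaves out 30 seconds. No section calls 30 seconds secondary or supportive, and none ranks the Synopsis against the body of the protocol.

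**2. The plan's own figure.** With 75 subjects, two treated sides per body area and three products, 75 × 2 / 3 = 50 sites per product per body area. This matches Section 9.2.

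**3. Tests that must be passed**

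- Synopsis: 2 body areas × 1 time = 2 per product, or 4 for A and B together.
- Section 2.1: 2 body areas × 2 times = 4 per product, or 8 for A and B together.

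The Section 2.1 tests include the Synopsis tests, so the Section 2.1 rule can never be the easier one.

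**4. Can the difference be turned into a probability?** Not from the documents, which give no SD, no correlation between times and no expected difference. The following shows scale only.

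Assumptions: true difference 0, 50 sites per product, independent body areas, pairing within subjects ignored, and correlation r of 0.3 to 0.9 between the estimates at the two times. SE = SD × √(2/50). The critical t is 1.976 (150 sites − 4 parameters = 146 df). With z = 0.5/SE − 1.976, the chance of meeting the rule is Φ(z)² at 10 minutes alone and Φ₂(z, z; r)² at both times.

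Worked case, SD 0.8: SE = 0.8 × 0.2 = 0.16; z = 3.125 − 1.976 = 1.149; Φ(z) = 0.875; squared, 76.5%.

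| Assumed SD (log10) | 10 minutes only | Both times, r 0.3 to 0.9 | Gap (points) |
|---|---|---|---|
| 0.5 | 99.75% | 99.51–99.61% | 0.1–0.2 |
| 0.6 | 97.17% | 94.57–95.94% | 1.2–2.6 |
| 0.8 | 76.50% | 60.90–70.22% | 6.3–15.6 |
| 1.0 | 48.96% | 27.86–40.62% | 8.3–21.1 |
| 1.2 | 29.44% | 11.73–22.21% | 7.2–17.7 |

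Pairing matters at the smaller SDs. Assume a within-subject correlation of 0.5 and subjects split 25/25/25 over the three product pairs. The sampling SD of A minus C is then SD × √(0.04 − 0.02 × 0.5), with the model SE unchanged. At SD 0.6 the gap falls from 1.2–2.6 to about 0.5–1.1 points; at SD 1.0 it is almost unchanged. A gap that runs from near zero to about 21 points on unsupported inputs does not give a size for this trial.

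**The case against.** The strongest reply is that the rest of the document already supplies the answer. The Synopsis objective names both times, both analysis descriptions fit a model at each, and the estimate is then held against the non-inferiority criteria. Read as a whole, even the Synopsis appears to apply the margin at 30 seconds. One sentence stands against several, in a summary, and no analysis changes either way.

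Most of this stands. The omission is probably a drafting slip, and the text favours Section 2.1. What remains is narrower. The analysis text refers back to criteria that are written in two ways, and it does not say that missing the bound at 30 seconds alone means immediate efficacy is not shown. Section 2.1 says so, the Synopsis criterion does not, and no order of precedence is given.

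A reader might go further and infer that the plan treats 10 minutes as sufficient and 30 seconds as secondary. The documents do not support that: the Synopsis criterion is silent on 30 seconds, and nothing demotes that time. A reader might also take the probabilities above as the cost of the conflict. They show how much stricter four tests are than two under assumed inputs, which is a different question.

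**Conclusion.** The two statements of the success rule conflict as written and should be reconciled. Two versus four required tests per product is certain and rests on no assumption. Section 2.1 is very probably the intended version, but that is an inference from the surrounding text. The consequence is confined to a product that passes at 10 minutes in both areas and fails at 30 seconds in at least one; in every other outcome the versions agree. How likely that pattern is cannot be derived from the documents. The models, sampling times and data are unaffected, so this is a defect in the decision rule that should be fixed, and it does not undermine the analysis.

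**What to change.** Before counts are linked to treatment assignments:

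1. Amend the Synopsis criterion to name 30 seconds and 10 minutes, as Section 2.1 does.
2. State in Section 9.3.1 and in the Synopsis statistical methods that the upper limit must be below 0.5 log10 at both times on both body areas, and that failure at either time means the criterion is not met.

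If the sponsor meant 10 minutes alone, changing Section 2.1 is not enough. The Synopsis objective sentence, the Synopsis statistical methods and Section 9.3.1 must be amended with it, and 30 seconds labelled as secondary. Otherwise the 30-second estimate is still compared with the non-inferiority criteria.

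The cost is a short text amendment, with no added subjects, samples or models. The drawback of the first route is that requiring both times is the stricter rule, so the chance of success is lower by an amount that the documents do not allow one to state.

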## Abbreviations

AE	Adverse event
AIDS	Acquired immune deficiency syndrome
ASTM	American Society for Testing Materials
ATCC	American Type Culture Collection
ATE	Average treatment effects
CFR	Code of Federal Regulations
CFU	Colony Forming Units
CHG	Chlorhexidine gluconate
cm 	Square centimeter
CRF	Case Report/Record Form
ER	EUROFINS EVIC PRODUCT TESTING ROMANIA S.R.L.
FDA	Food and Drug Administration
GCP	Good Clinical Practice
HIV	Human immunodeficiency virus
IB	Investigator's brochure
ICF	Informed consent form
ICH	International Conference on Harmonization
IEC	Institutional Ethics Committee
IPA	Isopropyl Alcohol
IRB	Institutional or Independent Review Board
MRSE	methicillin-resistant Staphylococcus epidermidis
MSSE	methicillin-sensitive Staphylococcus epidermidis
PBW	Phosphate Buffered Water
PDI	Professional Disposables International Inc.
PI	Principal Investigator
SAE	Serious adverse event
SOP	Standard Operating Procedure
SSF++	Stripping Suspending Fluid with product neutralizers
TSA	Trypticase Soy Agar
TSA+N	Trypticase Soy Agar containing neutralizers
TSB	Tryptic Soy Broth
US	United States of America

## 1 Introduction

Topical antimicrobial products are used prior to surgery in order to reduce the risk of nosocomial infection by reducing the number of microorganisms on the skin. Chlorhexidine gluconate (CHG) was first introduced in the United States in the 1970s as a hand washing agent for healthcare workers. Today, CHG is widely used as an effective antimicrobial for hand washing and patient skin antisepsis. The use of CHG for patient skin antisepsis was studied clinically by Maki et al. in the early 1990s. Maki compared the use of 2% aqueous CHG, 70% alcohol, and 10% povidone-iodine (a common iodophor) for patient skin preparation prior to placement of a central-line catheter. Aqueous 2% CHG formulation was found to significantly reduce the incidence of catheter-related infections, as compared to either 70% alcohol or 10% povidone-iodine. Moreover, Mimoza et al. showed CHG was more efficacious than povidone-iodine skin preparation in reducing contamination of blood cultures. In 2000, the first CHG and 70% isopropyl alcohol (IPA), was approved by the US FDA for patient pre-operative skin preparation. Since that time, numerous clinical studies support the use of the alcoholic CHG formulations, driving its wide adoption by clinicians worldwide.

The immediate and persistent antimicrobial efficacy of the investigational products will be evaluated in this study according to US FDA analysis criteria.

## 2 Study Objectives

### 2.1 Efficacy objectives

The objective of this study is to demonstrate immediate (30 seconds and 10 minutes) and persistent (6 hours) antimicrobial efficacy for patient preoperative skin preparation of product A and product B compared with product C.

To demonstrate the immediate antimicrobial efficacy at 30 seconds and 10 minutes post-application the following criteria should be met on both body area (abdomen and groin):

- non-inferiority of the ATE of the product A and product B compared to product C (the upper two-sided 95% confidence bound of the post-application microbial counts corrected for Baseline of the A-C or B-C should be less than  $0.5 \log_{10}$ ).

To demonstrate the persistent efficacy for patient preoperative skin preparation, the microbial counts ( $\log_{10}$  CFU/cm^2) at 6 hours post-application should be lower than or equal to the baseline for 100 percent of the subjects in each body area.

### 2.2 Safety objectives

Safety will also be evaluated based on the incidence of adverse events reported during the study and assessment of skin irritation ratings from [Appendix 17.8](#).

### **3 Study Design**

#### **3.1 Study Type**

This is a randomized, single-center, single blind study in healthy subjects. The staff member(s) performing bacterial enumeration will be blinded from the identification of treatment assignment.

#### **3.2 Endpoints**

- $\text{Log}_{10}$  CFU/cm^2 of skin flora at the abdominal and groin sites before and after each treatment at 30 seconds, 10 minutes and 6 hours.
- Skin irritation scores (Erythema, Edema, Rash, and Dryness) at each time interval and the incidence of AEs reported during the study.

#### **3.3 Randomization and Blinding**

The randomization scheme for the study will be provided by the Research facility.

Each subject will receive two treatments per body area. Assignment of products to the left or right side for each body area will be per a computer-generated randomization schedule.

Specific sites of sampling for baseline and post application sampling time points will be randomized on each body site (abdomen/groin and left/right).

Randomization will continue until required number of subjects with required treatment day baseline counts is enrolled.

The PI is responsible for ensuring that the randomization is followed. The randomization schedule for the abdominal and groin sites will be provided in a separate document. The study products will be labeled with the appropriate codes as designated by the study randomization.

Each subject will be identified by their initials and a subject number for which they qualify. Inclusion subject numbers will not be assigned until a subject has passed the screening criteria, including screening bacterial counts.

- Screening subjects will be assigned numbers starting with 001 and the letter "P": P001
- Treatment subjects will be assigned numbers with 001 and the letter "I": I001

The study products will not be blinded from the PI or other study staff performing the study material application or bacterial sample collections. The staff member(s) performing bacterial enumeration will be blinded from the identification of treatment assignment. The study staff performing the bacterial enumeration will not be involved in the study products application or the collection of samples. The Raw Data Sheet sections of the CRF will be maintained separately (from the pages within the CRF which include study treatment identifications) during the conduct phase of the study. The study staff performing the bacterial enumeration will record counts directly onto the Raw Data Sheet pages of the CRF without accessing the subject study documentation folder containing the other CRF pages. The Raw Data Sheets will be compiled with the entire CRF after all data recording have been completed.

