##### 5.1.3.1.1 Preparation of Abdomen Test Area

The test site within the abdominal region (abdominal test area) is defined as the area to the right and left sides of the abdomen, adjacent to the umbilicus that appear to be similar in condition and above the groin. The corners of each abdominal test area will be marked directly on the skin using a non-toxic skin marker. Four sampling sites will be numbered within each abdominal test area, on each side of the abdominal region. The positioning and numbering of the abdominal sampling sites are standard for all subjects. Sampling sites on the contra-lateral side of the abdomen will be numbered in a mirror-image orientation.

The four sampling sites within each abdominal test area represent one baseline (pre-prep) site and three post-prep sample sites (30 seconds, 10 minutes and 6 hours).

Test sites for study products and active control application on the abdomen will be 5" x 5" (12.7 cm x 12.7 cm) in area, occur on areas of skin to the right and left side of the navel, and should appear to be similar in condition.

After abdominal test areas are marked and sample sites numbered, baseline samples will be collected from the appropriate site per the randomization schedule in each test area using the scrub cup technique ([section 5.2.1](#)).

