### 5.1.3.2 Study Products Application

The randomization schedule will designate the treatment to each side of the abdomen and groin.

Following baseline sample collection, randomly assigned contra-lateral test areas will be treated with the applicable study products. The post-application sampling times will be randomized among the sampling sites within a test area.

The study products will be applied and the sampling configurations will be performed per the randomization scheme and the Treatment Application Instructions ([Appendix 17.6](#)). The duration of each application procedure will be recorded on the appropriate CRF. The study products, body sites, application and dry times and treatment area are summarized in [Table 2](#)[Table 2](#).

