### 17.3 Abdomen and Groin Diagram

#### 17.4 Randomization Scheme Example

The randomization will be provided in a separate document.

Randomization number	Body Area	Product Left Side	Product Right Side	Site 1	Site 2	Site 3	Site 4

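### Treatment Day baseline samples are collected by staff not blinded to side assignment, although counting is blinded; the assignment could be withheld until baseline collection is complete

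*Combined protocol and SAP*

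**What the plan says.** On who is blinded, section 3.3 says: "The study products will not be blinded from the PI or other study staff performing the study material application or bacterial sample collections". The protection lies downstream of collection: "The staff member(s) performing bacterial enumeration will be blinded from the identification of treatment assignment", and "The study staff performing the bacterial enumeration will not be involved in the study products application or the collection of samples". Section 3.3 also keeps the raw count sheets apart from the CRF pages that identify treatment.

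On the order of events, section 5.1.3.1.1 has the abdominal "baseline samples will be collected from the appropriate site per the randomization schedule in each test area", and 5.1.3.1.2 says the same for the groin. Section 5.1.3.2 makes that schedule the source of the product as well: "The randomization schedule will designate the treatment to each side of the abdomen and groin". Application comes second: "Following baseline sample collection, randomly assigned contra-lateral test areas will be treated with the applicable study products". The example layout in 17.4 has one row per randomization number and body area, with "Product Left Side" and its right-side counterpart beside Sites 1 to 4. The actual schedule is a separate document.

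On how the baseline count is used:
- It determines inclusion in the analysis: 3.11 to 5.50 log10 on the abdomen and 5.00 to 7.50 on the groin (9.1).
- It is the only covariate in the 30-second and 10-minute models (9.3.1).
- It is the threshold for success at 6 hours (9.3.1).

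**The concern.** Each subject receives two products, one on each side of a body area. A collector who knows the assignment therefore knows which side will carry the test product whenever A or B is paired with C. The scrub in 5.2.1 is done by hand. Cup, fluid volume and time are fixed, but pressure is specified only as moderate, so recovery can vary with the operator. Blinded counting protects the reading of the plate; it cannot correct what went into the tube.

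If recovery at baseline were systematically higher on the A or B side, the covariate adjustment would credit that side with a harder starting point and lower the A-C or B-C difference, which favours non-inferiority. The 6-hour threshold and the reported log reductions would move the same way.

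After application, masking the collector is difficult, because application technique (17.6) and, for product A, drying time (Table 2) differ from the control. Neither obstacle exists at baseline, so this exposure is avoidable.

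**Working it through.** **1. The plan's own figure.** 75 subjects x 2 treated sides per body area / 3 products = 50 sites per product, as in 9.2. The point does not affect this number. Section 9.2 gives no power, SD or effect size to reproduce.

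**2. What is open and what is masked at baseline.**

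| Step | Status in the documents |
|---|---|
| Choice of baseline site | Randomized (3.3) |
| Scrub | Collector not blinded (3.3) |
| Plate counting | Blinded, by separate staff (3.3) |
| Qualification | Read from those counts (17.2.1) against fixed limits (9.1) |
| When the collector first sees product by side | Not stated |

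Only the scrub is exposed.

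**3. Effect on the non-inferiority comparison.** In the 9.3.1 model, with post-treatment count y, baseline x and common slope b, the adjusted difference is

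(mean y_test - mean y_C) - b x (mean x_test - mean x_C).

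Adding a constant d to every test-side baseline leaves the within-product slope unchanged and moves the adjusted difference by -(b x d). Neither b nor d is in the documents. Assumed ranges give the following shifts, with the percentage of the 0.5 margin in brackets:

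| Slope | d = 0.1 | d = 0.2 | d = 0.3 |
|---|---|---|---|
| 0 | 0 | 0 | 0 |
| 0.2 | -0.02 (4%) | -0.04 (8%) | -0.06 (12%) |
| 0.25 | -0.025 (5%) | -0.05 (10%) | -0.075 (15%) |
| 0.5 | -0.05 (10%) | -0.10 (20%) | -0.15 (30%) |

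For scale, d = 0.1 is 10^0.1 = 1.26 times the recovery, and d = 0.3 is about 2.0 times.

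**4. Effect on the error rate.** Simulation of 4,000 trials, true difference at the 0.5 margin, 50 sites per product treated as independent, assumed baseline SD 0.6 and residual SD 1.0. The entries are the percentage of trials that wrongly conclude non-inferiority (nominal 2.5%):

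| Slope | d = 0 | d = 0.1 | d = 0.2 | d = 0.3 |
|---|---|---|---|---|
| 0.25 | 2.35 | 3.22 | 4.22 | 5.58 |
| 0.5 | 2.42 | 4.12 | 6.95 | 10.15 |

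The mean shifts in the simulation (-0.023, -0.051, -0.076 and -0.048, -0.098, -0.147) agree with the formula.

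**5. Effect at 6 hours.** Success is a 6-hour count no greater than baseline. Raising baseline by d changes the result only for a site whose 6-hour count lies above its true baseline by no more than d. The dilutions in 5.2.2 imply that most sites are expected well below: groin 10^-3 to 10^-5 at baseline against 10^0 to 10^-3 at 6 hours, abdomen 10^-1 to 10^-3 against 10^0 to 10^-2.

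**6. Effect on qualification.** The windows in 9.1 have an upper as well as a lower limit, so a harder scrub can move a site out as well as in. No direction of bias follows.

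**7. Comparison with post-application sampling.** A differential recovery of the same size d at 30 seconds or 10 minutes enters the dependent variable and shifts the difference by the full d. At slopes of 0.2 to 0.5, the baseline route is one-fifth to one-half of that.

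**The case against.** The strongest reply is that little is left exposed. The site is randomized, the cup, volumes and scrub time are fixed under a named ASTM method, and counters are blinded and separate from collectors. Nothing in the documents suggests that operators scrub one side harder, and the upper end of the range multiplies two assumed values. The same unblinded staff take the post-application samples, where a bias would count in full, so masking baseline gives only partial protection. All of this stands. It limits the size of the point but does not supply a reason to leave the baseline scrub open.

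Three stronger readings are tempting and not supported:

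- A reader might infer that the covariate, the qualification and the 6-hour threshold are all measured unblinded. Collection is open; counting is not, and qualification applies fixed limits to blinded counts. Both sides must also have met the screening minimum already (section 4).
- A reader might infer that collectors are shown to know the assignment when they scrub. This is a reasonable inference from 3.3, 5.1.3.1 and 17.4, but 17.4 is an empty example and no section says when the assignment is disclosed. What the documents establish is that collectors are not blinded and that nothing delays disclosure.
- A reader might infer a material threat to the 6-hour claim, because section 2.1 asks for success in 100 percent of subjects and one site could decide it. That requires a site close to its baseline count, and the documents give no frequency for this. Section 9.3.1 summarizes the rates descriptively.

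**Conclusion.** The point holds in a limited form. Section 3.3 leaves baseline collection unblinded at a stage where masking is practicable, and no section withholds the side assignment until baseline is taken. The exposure is confined to manual scrub technique.

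On assumed d of 0.1 to 0.3 and slope of 0.2 to 0.5, the adjusted difference would move by 0.02 to 0.15 log10, or 4% to 30% of the 0.5 margin. With a slope near zero, this route almost disappears. The simulated error rates rest further on assumed SDs and independent sites. The existence and direction of any differential recovery are hypothetical. At 6 hours the threshold would move by d, which matters only for sites near their baseline count.

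This is an inexpensive improvement that closes one avoidable route. It is not evidence that the comparison is biased, and the larger post-application route stays open.

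**What to change.** Issue the same randomization as two lists per randomization number: one with the order of sampling sites, one with product by side. Give collection staff only the first list until the Treatment Day eligibility form, the pre-baseline irritation score and both the left and right baseline samples for every body area treated that day are complete. Then release the product list and proceed to application.

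State this sequence in 3.3 and 5.1.3.1, and separate the product columns from the site columns in 17.4. If the site already works this way, the change only records it.

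The cost is protocol wording and a small handling step when the second list is released. The documents do not describe staffing or workflow, so that cost is a judgement. Sample size, margin, alpha, model and study procedures are unchanged. The change does not address open-label sampling after application, and the report should say so.
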